### 3.3.5 Replacement of patients

SRD part:

Patients withdrawn before visit 4 for another reason than DLE or patients who miss any visit from Visit 2 up to and including Visit 4 are not evaluable for the occurrence of a DLE within 7 days after drug administration. These patients will be replaced if not decided otherwise by the SMC. Patients who come off study due to a DLE will not be replaced.

MD part:

If some patients do not complete the trial, the Clinical Trial Leader together with the Trial Pharmacokineticist and the Trial Statistician are to decide, if and how many patients will be replaced.

A replacement patient will be assigned a unique trial patient number and will be assigned to the same treatment as the patient he or she replaces.

## 4. TREATMENTS

### 4.1 INVESTIGATIONAL TREATMENTS

#### 4.1.1 Identity of the Investigational Medicinal Products

Table 4.1.1: 1 BI 764524

Substance:	BI 764524
Pharmaceutical form:	██████████ for injection
Source:	Boehringer Ingelheim Pharma GmbH & Co. KG
Unit strength:	██████████
Posology:	SRD part: 1 injection MD part: 3 injections, each separated by 4 weeks
Mode of administration:	Intravitreal

Table 4.1.1: 2 Diluent

Substance:	Solvent for dilution of BI 764524 solution for injection ██████████
Pharmaceutical form:	Solvent
Source:	Boehringer Ingelheim Pharma GmbH & Co. KG
Unit strength:	n/a
Posology:	SRD part: 1 injection
Mode of administration:	Intravitreal

#### 4.1.2 Selection of doses in the trial and dose modification

The measurement of the avascular area in the mouse model of oxygen-induced retinopathy is an animal surrogate to evaluate the effect of Sema3A inhibition on revascularization of an ischemic retinal area supporting the therapeutic benefit in DMI patients. In an in-house study using such a model (n00262705) ██████████ BI 764524 administered intravitreally into the mouse eye resulted in a reduction of the avascular area over a period of 5 days.

A rabbit IVT PK study was performed with ██████████ BI 764524 (n00270338-01) and the rabbit vitreous half-life of 4 days is in good agreement with that previously reported for other Boehringer Ingelheim (BI) ██████████. Furthermore, the ██████████ in the rabbit vitreous was completely bound after IVT injection of BI 764524 over the whole study period of 4 weeks and no free ██████████ was present indicating that its activity would be blocked as long as the ██████████.

Human dose prediction is based on the fact that the PK of BI 764524 is similar to [REDACTED] in the rabbit and is thus expected to be similar to [REDACTED] also in humans. An IVT half-life of [REDACTED] days has been described for [REDACTED] ([R18-2968](#)). The minimum effective concentration is estimated as the upper range (about 1 nM) of the described [REDACTED] concentration in the vitreous for patients with DME and PDR ([R17-3888](#), [R17-3904](#)).

Using these values, the proposed starting dose of [REDACTED] is predicted to maintain the minimal efficacious vitreal concentration of 1 nM for 93 days. Doses lower than [REDACTED] are also expected to induce PD effects in the eye. However, the duration of the effect would be shorter and might not be long enough to justify a potential sufficiently long benefit to the patients.

The proposed escalation of the doses to [REDACTED], and [REDACTED] per eye is predicted to prolong the time for [REDACTED] concentrations above the estimated minimally efficacious concentration to 103 days and 116 days respectively. The final dose range was chosen based on the safety margin to the no observed adverse effect level (NOAEL), of the 13-week IVT study in cynomolgus monkeys. The [REDACTED] dose is expected to last only 9 days longer in the vitreous than the [REDACTED] dose and requires an injection volume of [REDACTED] ml. Therefore, a decision was made to remove the [REDACTED] dose from the trial.

Table 4.1.2: 1 Provisional dose levels for escalation

Dose level	Proposed dose	Relative increment from previous dose
1	[REDACTED]	Starting dose
2	[REDACTED]	100%
3	[REDACTED]	150%

### 4.1.3 Method of assigning patients to treatment groups

After the assessment of all in- and exclusion criteria, patients will be enrolled into the SRD and MD part. Recruitment in the trial will start with the lowest dose group of the SRD part. The MD part will recruit patients only after the SRD part has been completed and safety of the doses has been established.

In the SRD part, the dose is planned to be escalated in cohorts at the pre-defined provisional dose levels; see Table 4.1.2: 1. Intermediate or lower dose levels, depending on the number of DLEs observed in the study, as long as they fulfil the EWOC criterion, may be investigated if agreed upon between Investigator and Sponsor. At the end of each treatment cohort, BI will convene a meeting with the SMC members. At the dose escalation meeting, the clinical course for each patient in the current dose cohort will be reviewed in detail. Based on that and on the results of the updated BLRM, a decision on the next dose level to be tested is made.

In general, recruitment for the SRD part will be done successively for the dose groups, i.e. if the required number of patients for one dose group is completed and this dose is considered safe based on (the BLRM model and) the clinical course, the recruitment of the next higher dose group may be started. Therefore, the recruitment of patients for the dose groups will neither be influenced by the trial personnel nor by any characteristics of the patients, but only by temporal availability. Patients from the SRD part are not allowed to participate in the MD part.

The highest dose (██████) if established as safe and tolerable during the SRD part will be used in the MD part after the SRD part has been completed. In the MD part patients will be randomized to receive either active treatment or sham injection according to a randomization plan at visit 2 via Interactive Response Technology (IRT). 20 patients on treatment and 10 on sham injection.

The randomization procedure is described in Section [7.6](#).

#### 4.1.4 Drug assignment and administration of doses for each patient

BI 764524 will be administered intravitreally. “BI 764524 ██████████ for injection ██████████” and “Solvent for dilution of BI 764524 Solution for Injection” will be provided by BI. A site pharmacist (qualified person) will prepare the ready to use drug product according to the “Instructions to Pharmacist”. The instructions will be provided by BI and will be filed in the ISF.

Table 4.1.4: 1 Planned doses and treatment schedule for the SRD part

Dose group (mg)	Visit 2 Day 1
██████	X
██████	X
██████	X

To determine the dose regimen for the next cohort, the available toxicity information (including DLEs and AEs that are not DLEs), PK, PD, as well as the recommendations from the BLRM will be evaluated by the SMC members at the dose decision meeting. The parties must reach a consensus whether further dose escalation is appropriate, or whether de-escalation and/or expanded recruitment into particular cohorts is appropriate. Minutes from these meetings will be prepared and circulated to the trial team and each investigator for comment prior to finalization. The next dose group will only be initiated after further dose

escalation is considered appropriate by the SMC (see Section 4.1.2 for details on dose rationale and escalation concept).

Table 4.1.4: 2 Planned dose and treatment schedule for the MD part

Dose group (mg)	Visit 2 Day 1	Visit 3 Day 29	Visit 4 Day 57	Visit 5 Day 85	Visit 6 Day 113
2.5	X	X	X		

#### 4.1.5 Intravitreal Injection Technique and Sham Injection

IVT injections must be carried out according to medical standards and applicable guidelines by a qualified physician experienced in administering IVT injections. In general, adequate anaesthesia and asepsis, including topical broad-spectrum microbicide (e.g. povidone iodine applied to the periocular skin, eyelid and ocular surface) have to be ensured. Surgical hand disinfection, sterile gloves, a sterile drape, and a sterile eyelid speculum (or equivalent) are recommended.

The MD part is designed single-masked and personnel of the trial site are masked. Therefore, in the MD part an unmasked injector with no other involvement in the trial will administer IVT/sham injections.

For a sham injection, all pre- and post-injection procedures are identical compared to IVT injections. For a sham injection, the hub of a syringe without a needle is pressed against the conjunctival surface to simulate the force of an actual injection. For sham aqueous sampling, all procedures are identical to aqueous sampling, the hub of a syringe without a needle is pressed gently against the corneal surface to simulate aqueous sampling.

Use of antibiotics in the pre-, peri-, or post-injection period is at investigator's discretion.

After administration of BI 764524, patients will be monitored according to standard practice and at least for 1 hour. In this minimum post-dose observation period, systemic and ocular conditions will be monitored according to local practice for such procedures.

#### 4.1.6 Masking and procedures for unmasking

##### 4.1.6.1 Masking

The SRD part of the trial is open label. The MD part is designed single-masked. The treatments administered (active or sham injection) will be masked to patients and to the dedicated personnel of the trial site. For the MD part, an unmasked pharmacist (qualified

person) will prepare the active IVT injection and an unmasked injector with no other involvement in the trial will administer active/sham injections.

This single-masked design is considered acceptable because the potential bias in this type of study seems to be low and according to study procedures it is assured that the investigator's knowledge of the next treatment does not influence the decision to enter a patient.

At the sponsor site, all trial data will be handled open label. This means that trial functions of the sponsor are unmasked (including clinical monitor, data manager, statistician, bioanalyst, pharmacokineticist, pharmacometrician, drug metabolism scientist).

Within the central ECG lab, readers involved with interval measurements will be masked with respect to treatment, visit and demographic information collected.

If an interim safety analysis of ECG data is required, a part of the staff of the central ECG lab may be unmasked.

#### **4.1.6.2 Unmasking and breaking the code**

Emergency unmasking will be available to the investigator via Interactive Response Technology (IRT) system. It must only be used in an emergency situation when the identity of the trial drug must be known by the investigator in order to provide appropriate medical treatment or otherwise assure safety of trial participants. The reason for unmasking must be documented in the source documents and/or appropriate CRF.

#### **4.1.7 Packaging, labelling, and re-supply**

The investigational products will be provided by BI or a designated Contract Research Organization (CRO). They will be packaged and labelled in accordance with the principles of Good Manufacturing Practice (GMP). Re-supply to the sites will be managed via an Interactive Response Technology (IRT) system, which will also monitor expiry dates of supplies available at the sites.

For details of packaging and the description of the label, refer to the ISF.

#### **4.1.8 Storage conditions**

Drug supplies will be kept in their original packaging and in a secure limited access storage area according to the recommended storage conditions on the medication label. A temperature log with min-max recordings must be maintained for documentation.

If the storage conditions are found to be outside the specified range, the Clinical Trial Manager (as provided in the list of contacts) must be contacted immediately.

#### 4.1.9 Drug accountability

The investigator or designee will receive the investigational drugs from the sponsor when the following requirements are fulfilled:

- Approval of the clinical trial protocol by the IRB / EC
- Availability of a signed and dated clinical trial contract between the sponsor and the investigational site
- Approval/notification of the regulatory authority, e.g. competent authority (CA)
- Availability of the *curriculum vitae* of the Principal Investigator
- Availability of a signed and dated clinical trial protocol
- Availability of the proof of a medical licence for the Principal Investigator (If applicable)
- Availability of FDA Form 1572 (If applicable)

Investigational drugs are not allowed to be used outside the context of this protocol. They must not be forwarded to other investigators or clinics.

The investigator and/or pharmacist (qualified person) and/or investigational drug storage manager must maintain records of the product's delivery to the trial site, the inventory at the site, the use for each patient, and the return to the sponsor or warehouse / drug distribution centre or alternative disposal of unused products. If applicable, the sponsor or warehouse / drug distribution centre will maintain records of the disposal.

These records will include dates, quantities, batch / serial numbers, expiry ('use- by') dates, and the unique code numbers assigned to the investigational product and trial patients. The pharmacist (qualified person) / investigational drug storage manager will maintain records that document adequately that the patients were provided the doses specified by the CTP and reconcile all investigational products received from the sponsor. At the time of return to the sponsor and/or appointed CRO, the investigator or designee must verify that no remaining supplies are in the investigator's possession.

## 4.2 OTHER TREATMENTS, EMERGENCY PROCEDURES, RESTRICTIONS

### 4.2.1 Other treatments and emergency procedures

There are no special emergency procedures to be followed.

### 4.2.2 Restrictions

#### 4.2.2.1 Restrictions regarding concomitant treatment

Medications listed under the exclusion criteria (Section [3.3.3](#)) are restricted during the trial.

For the Study eye no other treatment (IVT or otherwise) is allowed during the trial. The fellow eye can be on any on label drug. The Sponsor will not provide fellow eye treatment or compensate for it.

Any intravitreal treatment and use of medications known to be toxic to the retina, lens or optic nerve (e.g. desferoximine, chloroquine/hydrochloroquine, chlorpromazine, phenothiazines, tamoxifen, nicotinic acid, and ethambutol) are restricted during the trial.

#### **4.2.2.2** Restrictions on diet and lifestyle

None

#### **4.2.2.3** Contraception requirements

WOCBP (for the definition please refer to Section [3.3.2](#)) and men able to father a child must use two medically approved methods of birth control throughout the trial (from Visit 1 until End of Study visit) one barrier method (condom), and one highly effective non-barrier method.

Men (trial participant or partner of a trial participant) must use a condom (regardless of vasectomy) if their sexual partner is a WOCBP.

WOCBP (trial participant or partner of a trial participant) must use a highly effective method of birth control per ICH M3 (R2) throughout the trial (from Visit 1 until EOS visit) that results in a low failure rate of less than 1% per year when used consistently and correctly if their sexual partner is a man able to father a child.

- Combined (estrogen and progestogen containing) hormonal birth control that prevents ovulation (oral, intravaginal, transdermal).
- Progestogen-only hormonal birth control that prevents ovulation (oral, injectable, implantable).
- Intrauterine device (IUD) or intrauterine hormone-releasing system (IUS).
- Bilateral tubal occlusion

Or

Patients must abstain from male-female sex if this is defined as being in line with the preferred and usual lifestyle of the patient. Periodic abstinence e.g. calendar, ovulation, symptothermal, post-ovulation methods; declaration of abstinence for the duration of exposure to study drug; and withdrawal are not acceptable.

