#### **4.2.2.4** Restrictions regarding gamete donation

Gamete donation must not be performed from the time of the first dose of the investigational drug, and for at least 3 months after the last dose of the investigational drug.

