## **6.2.3 Follow-up period and trial completion**

Patients must continue to be followed according to the visit schedule (unless they withdraw consent for further follow-up) in order to collect data at the end of the planned observation period. Unscheduled visits will be possible at the discretion of the investigator at any time for safety reason. The unscheduled visit may include any assessments considered necessary by the investigator. All unscheduled visits should be described and documented in the medical /source record. The investigator may decide other treatment options during the follow-up period as deemed medically appropriate.

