### SRD part

#### Visit 8/End of Study:

The Visit 8/EOS will be performed 42 days after Visit 7 (see Flow Chart I).  
The Visit 8/EOS is the final visit and the End of Study CRF has to be completed.

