### Withdrawal of consent

Every effort should be made to keep the patient in the trial and undergoing the procedures and follow up as outlined in the [Flow Charts I](#) and II and Section [6.2.3](#).

If a patient is not willing to continue in the trial and wants to withdraw consent prior to the end of the study, Visit 7 (SRD part)/ Visit 6 (MD part) should be scheduled as soon as possible, and also Visit 8/EOS(SRD part)/ Visit 7/EOS(MD part) should be performed to assess for safety.

The End of Study eCRF has to be filled in even if patient refuses to participate to the above specified visits.

For AE assessment, laboratory tests, recording of ECG and vital signs, and physical examination during the follow-up period, see Section [5.2](#).

Patients who discontinue treatment before the end of the planned treatment period should undergo the EOS Visit.

All abnormal values (including laboratory parameters) that are assessed as clinically relevant by the investigator will be monitored using the appropriate tests until a return to a medically acceptable level is achieved. (S)AEs persisting after a patient's EOS Visit must be followed until they have resolved, have been sufficiently characterised, or no further information can be obtained.

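### Contraception ends at the End of Study visit with no minimum time after the last dose, so early leavers can stop inside the 3 months set for gamete donation

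*Protocol*

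**What the plan says.** Protocol Section 4.2.2.3 requires that women of childbearing potential, and men who can father children, "must use two medically approved methods of birth control throughout the trial (from Visit 1 until End of Study visit"). The paragraph on highly effective methods repeats the same end point. Inclusion criterion 7 in both parts refers back to this section and adds no duration.

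The next section, 4.2.2.4, counts from the last dose instead: gamete donation is barred "for at least 3 months after the last dose of the investigational drug". The 3 months is stated for donation only.

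Section 6.2.3 governs when EOS takes place:

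- In general: "Patients must continue to be followed according to the visit schedule (unless they withdraw consent for further follow-up").
- On the regular single rising dose (SRD) schedule: "The Visit 8/EOS will be performed 42 days after Visit 7". The multiple dosing (MD) part has the same 42-day spacing between Visit 6 and Visit 7.
- On withdrawal of consent, for the penultimate visit: "Visit 7 (SRD part)/ Visit 6 (MD part) should be scheduled as soon as possible". For EOS itself the text then adds, without a date: "and also Visit 8/EOS(SRD part)/ Visit 7/EOS(MD part) should be performed to assess for safety".
- If the patient declines: "The End of Study eCRF has to be filled in even if patient refuses to participate to the above specified visits".
- On early stop of treatment: "Patients who discontinue treatment before the end of the planned treatment period should undergo the EOS Visit". Section 3.3.4.1 keeps MD patients who stop treatment on Flow Chart II only if they agree.

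Section 1.2.1 states that the residual effect period is unknown.

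**The concern.** Two adjacent rules that both guard against reproductive exposure run on different clocks. Donation is tied to the last dose. Contraception is tied to a visit, and that visit can move or never happen. Under the contraception rule, a patient who leaves early may therefore be released sooner after dosing than the donation rule would allow, or may be given no end date at all.

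What is at stake is participant protection in a first-in-human trial. The absolute risk is probably small. Section 1.4.2 expects very low systemic exposure, few patients are concerned, and Section 5.2.7.2.3 requires drug exposure during pregnancy to be reported within 24 hours. That last measure reports an exposure and does not prevent one.

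**Working it through.** **Inputs.** SRD: dose on Day 1, EOS on Day 99 ± 7 (Flow Chart I, Table 10.1: 1). MD: injections on Day 1, Day 29 ± 3 and Day 57 ± 3, EOS on Day 155 ± 7 (Flow Chart II, Table 10.1: 2). Spacing from penultimate visit to EOS: 42 days (Section 6.2.3). Assumption: 3 months = 91 days; three calendar months range from 89 to 92.

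**The plan's own figure.** Sections 1.4.2.4 and 3.1 give follow-up of up to 98 days. SRD: 99 − 1 = 98. MD: 155 − 57 = 98. Both reproduce.

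**Completers, last dose to EOS within visit windows.**

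- SRD: (99 − 7) − 1 = 91 to (99 + 7) − 1 = 105 days.
- MD: (155 − 7) − (57 + 3) = 88 to (155 + 7) − (57 − 3) = 108 days.
- Largest shortfall: 91 − 88 = 3 days in the MD part (1 to 4 days over the range 89 to 92).

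**Withdrawal of consent.** Let w be the days from the last dose to the brought-forward visit. The text admits three readings of when EOS follows.

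1. *EOS on its planned day.* 98 days nominal in SRD and after the third MD injection; 155 − 29 = 126 after two MD injections; 155 − 1 = 154 after one. No shortfall.
2. *42-day spacing kept.* EOS falls at w + 42. This is inside 91 days when w < 91 − 42 = 49 (w < 47 to w < 50 over the range 89 to 92). In study days, that means a brought-forward visit before Day 50 in SRD, or before Day 57 + 49 = 106 after the third MD injection.
3. *EOS done at once.* EOS falls at w, inside 91 days for any w < 91: before Day 92 in SRD, or before Day 57 + 91 = 148 after the third MD injection. This has the least textual support, because the urgency is written only for the penultimate visit.

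| w (days) | EOS, reading 2 | Short of 91 | EOS, reading 3 | Short of 91 |
|---|---|---|---|---|
| 3 | 45 | 46 | 3 | 88 |
| 14 | 56 | 35 | 14 | 77 |
| 28 | 70 | 21 | 28 | 63 |

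For a patient who leaves between MD injections, with the visit before the next injection would be due, w is at most (57 + 3) − (29 − 3) = 34. Reading 2 then gives at most 34 + 42 = 76 days, which is at least 15 days short.

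**Visits refused.** There is no EOS visit, so a rule that runs until that visit gives no end date.

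**The case against.** The strongest reply is that the gap depends on a reading the protocol does not require. EOS is a scheduled visit with a fixed study day, and the urgency applies only to the visit before it. With EOS on its planned day, contraception lasts 98, 126 or 154 days, and that day could serve as the end date even for someone who does not attend. Patients who only stop treatment normally stay on the visit schedule, so their EOS comes later relative to the last dose, not earlier.

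Three further points have weight. No section says contraception must match the donation period, and Global Amendment 2 edited the contraception sentence without changing its end point. Advice to someone who has withdrawn consent cannot be enforced and belongs naturally in the patient information. That document was not available for review and may give a date.

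Much of this stands: the planned-day reading removes the withdrawal shortfall, the 3-month benchmark is borrowed from the donation rule, and the patient information is unseen. It does not settle the matter. The protocol never selects the planned-day reading, it ties contraception to a visit and not to a study day, and it expressly foresees patients who do not attend. For someone who has withdrawn consent or declined further follow-up, the instruction to keep to the visit schedule no longer clearly applies.

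**Conclusion.** The concern holds as a minor participant-protection point. Section 4.2.2.3 has no post-dose minimum, and the exit rules in Section 6.2.3 do not supply one. Completers are covered apart from about 3 days at the MD window extreme. Early leavers may be 21 to 46 days short of 91 if the 42-day spacing is kept and the brought-forward visit falls 28 to 3 days after the last dose. They are not short at all if EOS keeps its planned day.

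The figures rest on 3 months being 91 days and on using the donation limit as the yardstick. Those affected are women of childbearing potential and men able to father a child who withdraw consent, decline follow-up or have an early EOS. SAP Section 6.1 reports 12 SRD and 32 MD patients enrolled and 3 discontinued, without reasons or timing, so the number actually affected cannot be stated. No endpoint or analysis changes.

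**What to change.** In Section 4.2.2.3, require contraception until the later of the EOS visit or 3 months after the last injection, active or sham, so that the instruction does not reveal treatment. In Section 6.2.3, state that patients who withdraw consent or refuse the EOS visit are told this date when they leave. If the patient information already gives an end date, align the wording with it.

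The cost is one sentence in each section. Some early leavers would be asked to continue for several more weeks: for w = 3, 46 more days if the 42-day spacing is kept, or 88 if EOS is done at once. This includes sham patients who received no drug. An MD completer at the window extreme would continue for about 3 more days. After consent is withdrawn the date is advice only. Since SAP Section 6.1 reports recruitment complete, the benefit is to patients still in follow-up and to later protocols for this compound.
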